INVESTIGATIONAL PRODUCT AND PLANNED USE	To evaluate the (1) Feasibility of the Ready-Heat® blanket to increase temperature by at least 1°C at eight hours from arrival to the trauma bay in severely injured trauma patients to whom a massive hemorrhage protocol is activated; (2) Feasibility of adherence to the application of the Ready-Heat® blanket in patients enrolled in the intervention arm throughout the trauma bay resuscitation; (3) Feasibility of adherence to body temperature measurement throughout the different phases of care (i.e.: TB, ED, CT scanner suite, OR, IR suite, ICU) ; (4) Feasibility of maintenance of at least one Ready-Heat® blanket applied throughout the different phases of care (i.e.: TB, ED, CT scanner suite, OR, IR suite, ICU)
STUDY DESIGN	A phase I, single center, pilot, feasibility, prospective, open-label RCT
DURATION OF FOLLOW-UP	From first application of study product to final study visit = 8 hours
TREATMENT ALLOCATIONS	Experimental arm: 2 Ready-Heat® 4-panel blankets Control arm: standard of care (use of warmed blankets and forced air warmed blanket [FAWB])
PATIENT POPULATION	Adults (\geq 16 years old) patients presenting to Sunnybrook Health Sciences Centre (SHSC) as trauma team activations to whom a massive hemorrhage protocol is activated
SETTING	Single academic Level 1 trauma center
PLANNED SAMPLE SIZE	74 patients (37 on each study arm) The anticipated duration for this study's recruitment period is 24 months.
PATIENT INCLUSION/EXCLUSION	
Inclusion criteria:
 
 • Age \geq 16 years • Requires Massive Hemorrhage Protocol activation (see Table 1) in the trauma bay • Admission to the trauma bay between 08:00-20:00hrs on weekdays 
Exclusion criteria:
 
 • Transferred from another healthcare facility • Death in the trauma bay prior to randomization • Arrival to trauma bay with ongoing CPR • Patients with penetrating head injury with Glasgow Coma Scale of 3 AND loss of brain matter through the wound

RANDOMIZATION	Web-based computerized allocation sequence generated by independent statistician
STUDY OUTCOMES	
Primary outcomes (feasibility):
 
 (1) Feasibility of performing a pilot pragmatic randomized controlled trial (RCT) to evaluate effectiveness of the Ready-Heat® blanket to increase temperature by at least 1°C at eight hours from time of blanket placement in the trauma bay in severely injured trauma patients to whom a massive hemorrhage protocol is activated (2) Feasibility of adherence to the application of the Ready-Heat® blanket in patients enrolled in the intervention arm throughout the trauma bay resuscitation; (3) Feasibility of adherence to body temperature measurement throughout the different phases of care (i.e.: TB, ED, CT scanner suite, OR, IR suite, ICU) within the first eight hours of blanket application. (4) Feasibility of maintenance of at least one blanket applied throughout the different phases of care (i.e.: TB, ED, CT scanner suite, OR, IR suite, ICU) 
Secondary Measures:
 
 (1) Concurrent warming strategies used (i.e.: fluid warmers, FAWB, etc.) within the first eight hours of blanket application in conjunction with or replacement of Ready-Heat® chemical heating blanket; (2) Number of units of blood products (plasma, red blood cells, platelets, fibrinogen concentrate) transfused within 24 hours of trauma bay arrival; (3) Coagulation (platelet count, INR, fibrinogen) and perfusion parameters (pH, base deficit, serum lactate) measured on arrival, and at the next time points collected as per clinician discretion; (4) Hemoglobin level measured on arrival, and at the next time points collected as per clinician discretion. 
Secondary Safety Measures:
 
 (1) Number of times blanket is placed directly on the skin; (2) Skin redness and/or burns.
STATISTICAL ANALYSIS	
The results of this pilot trial will be used to assess the feasibility and inform the design of a definitive trial. We will present point estimates of feasibility outcomes with 95% confidence intervals.
 
Demographic and clinical characteristics will be summarized in total and by two arms using mean, standard deviation (SD), median (interquartiles) and range for continuous variables, and percentages for categorical

	
variables. The Wilcoxon rank-sum test, Chi-square test or Fisher exact test will be applied for comparing continuous or categorical variables between two arms, as appropriate. The proportion (and 95% confidence intervals) of patients with an increased temperature by at least 1°C at 8 hours from arrival to the trauma bay will be calculated and compared between two arms using Chi-square or Fisher exact test as appropriate. Linear mixed model will be used to search for significant time trends in two arms on the hourly body temperature measurements within the first eight hours of blanket application. To compare coagulation and perfusion parameters measured on arrival and over the first 8 hours, between two arms, linear mixed model will also be performed for the repeated measurements. P-value < 0.05 will be considered statistically significant.

--	---

[figure not shown]

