3.3 Secondary Feasibility Outcomes

2- Feasibility of applying and keeping the 2 blankets in the trauma bay
3- Feasibility of keeping the 2 blankets in the CT scanner suite
4- Feasibility of keeping the 2 blankets in the ED
5- Feasibility of keeping at least one of the blanket in the OR or IR suite (one can be removed for procedures and re-applied at the end of the intervention)
6- Feasibility of keeping the 2 blankets in PACU (for example one blanket is removed in the OR and reapplied at the end of the procedures and kept in PACU before the patient is transferred to the ICU)
7- Feasibility of keeping the 2 blankets in the ICU up to 8 hours of until patient achieves 37.5 degrees Celsius.
8- Reasons why the blanket was not maintained at each of the next phase of care (CT scanner suite, IR suite, OR, ED, ICU)

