5.4.1 Study Visits

The following information will be collected during study visits either in person or remotely reviewing electronic health records. During weekdays, 8 am to 8 pm, the research assistant will be following the patient across the different phases/locations of care and will be collecting data at the same time. Research assistants will access all documented data on the next weekday. Visits and specific data collection are detailed as follows:

5.4.1.1 Visit 1

On admission to the trauma bay: Demographics, injury characteristics and surgical management:

1. Date of injury
2. Time of injury
3. Sex
4. Age
5. Types of surgical procedures performed in the first 8 hours following hospital arrival
6. Date of arrival
7. Time of arrival
8. Time of randomization
9. Name of attending TTL and sub-TTL (if applicable)
10. Initial temperature recorded
11. Was the blanket placed on the patient? Yes/No
12. Time that the blanket was placed on the patient, if registered
13. Reason why blanket was not applied
14. Blanket applied directly to the patient's skin? Yes/No
15. Use of fluid warmers
16. Use of FAWB

5.4.1.2 Visit 2

Within the first eight hours of blanket application:

1. Location of the patient
2. Is the blanket kept on the patient? (Yes/No)
3. If not, what was the reason it was removed?
4. Temperature recorded, hourly (Yes/No)
5. If yes, the temperature recorded
6. Type of temperature measurement
7. Blanket applied directly to patient's skin? Yes/No
8. Use of FAWB
9. Use of fluid warmers

At discretion of the clinician, within the first eight hours of blanket application:

10. Coagulation (platelet count, INR, fibrinogen)
11. Perfusion parameters (pH, base deficit, serum lactate)
12. Hemoglobin

13. Number of units of red blood cells, plasma, platelets, and fibrinogen concentrate administered within the first 8 hours

5.4.1.3 Visit 3

At 24 hours post blanket application:

1. Number of units of red blood cells, plasma, platelets, and fibrinogen concentrate administered within the first 24 hours
2. Type of injury (blunt/penetrating)
3. Injury Severity Score (ISS)
4. Frequency of safety events with skin

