6.0 CRITERIA FOR OUTCOME ASSESSMENT

6.1 Primary outcome assessment

1. *Feasibility of Ready-Heat® blanket to increase temperature by at least 1°C at eight hours from arrival to the trauma bay in massively bleeding trauma patients.*
If the study intervention is unable to increase body temperature by at least 1°C in 80% of patients at eight hours from arrival, the study as it is currently designed will not be deemed feasible.
2. *Feasibility of adherence to the application of the Ready-Heat® blanket in patients enrolled in the intervention arm throughout the initial trauma bay resuscitation* Failure to apply and maintain the Ready-Heat® blanket in more than 20% of patients enrolled in the intervention arm throughout the initial trauma bay resuscitation, the study will not be deemed feasible.
3. *Feasibility of adherence to body temperature measurement throughout different phases of care within first eight hours of blanket application.*
Failure to measure body temperature throughout different phases of care (i.e.: ED, CT, OR, IR, ICU) within the first eight hours of blanket application in more than 20% of enrolled patients, the study will not be deemed feasible.

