9.1 Data Collection and Follow-up for Withdrawn Participants

Patients will be asked to continue with follow-up of body temperature and laboratory tests. It is important to continue to follow these patients and capture outcomes that occur once they have discontinued study intervention to determine feasibility. Through telephone calls and emails, every effort will be made to obtain permission to document the reason participants withdrew consent and to continue collecting the body temperature and laboratory values previously mentioned. Patients who have had at least one of the blankets applied will be included in the per-protocol analysis.

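### Feasibility criterion 2 does not say whether one or both blankets must stay on; Section 3.3 and the Summary differ for the trauma bay, and the listed yes/no items cannot tell the two apart

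*Combined protocol and SAP*

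**What the plan says.** Each intervention patient is issued two four-panel blankets (Summary, Treatment Allocations; Sections 5.1 and 5.3.3.2). How many must be on the patient is described differently from place to place:

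- **Section 6.1, criterion 2.** The failure event is "Failure to apply and maintain the Ready-Heat® blanket in more than 20% of patients enrolled in the intervention arm" during the initial trauma bay resuscitation. No number of blankets is given. This is the only blanket-adherence rule with a cut-off.
- **Summary, Study Outcomes (2).** "Feasibility of adherence to the application of the Ready-Heat® blanket in patients enrolled in the intervention arm", again for the trauma bay and again without a number.
- **Summary, Study Outcomes (4).** "Feasibility of maintenance of at least one blanket applied throughout the different phases of care". The phase list starts with the trauma bay. The planned-use row of the Summary says the same.
- **Section 3.3.** For the trauma bay: "Feasibility of applying and keeping the 2 blankets in the trauma bay". The CT, ED and PACU items also name two blankets, and so does the ICU item: "Feasibility of keeping the 2 blankets in the ICU up to 8 hours". The one exception is "Feasibility of keeping at least one of the blanket in the OR or IR suite".
- **Section 5.4.1, data items.** Visit 1 has a yes/no item on whether the blanket was placed. Visit 2 has "Is the blanket kept on the patient? (Yes/No"). Both refer to a single blanket.
- **Section 9.1.** "Patients who have had at least one of the blankets applied will be included in the per-protocol analysis".

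Section 7.2 does not define an adherence endpoint, so the analysis plan does not settle the matter.

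**The concern.** A patient who keeps one blanket in the trauma bay and loses the other meets Summary outcome (4) and does not meet the trauma-bay item of Section 3.3. Criterion 2 covers that same phase and does not say which way the patient counts.

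Such patients are expected by design. Sections 5.1 and 5.3.3.5 explain that two separate blankets are used so that one can come off for a procedure while the rest of the body stays covered. Neither section says whether that temporary removal is a failure to maintain.

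Two things are at stake. One of the three pass/fail rules in Section 6.1 could be settled by a definition chosen after the data are seen, in an open-label trial. And if the data are captured as listed, a yes may mean one blanket or two, so the two-blanket outcomes of Section 3.3 could not be recovered later.

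**Working it through.** **Inputs from the documents.** 74 enrolled, 37 per arm; 58 evaluable, 29 per arm; 80% planning compliance, ±10% precision, 20% dropout (Section 7.1); failure cut of more than 20% in the intervention arm (Section 6.1).

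**The plan's own figure.** The output table in Section 7.1 is exact binomial coverage, P(|x/n − 0.80| ≤ 0.10). For n = 57 this is P(40 ≤ x ≤ 51) = 0.95529, as printed. Then 58/(1 − 0.20) = 72.5, which rounds up to 73 and to 74 for equal arms; per arm 29/0.80 = 36.25, so 37. The stated sample size reproduces and does not depend on the blanket definition.

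**Where criterion 2 turns.**

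- n = 37: 7/37 = 18.9% passes; 8/37 = 21.6% fails.
- n = 29: 5/29 = 17.2% passes; 6/29 = 20.7% fails.

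**Worked example (assumed counts, n = 37).**

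| Both on | One only | None | Failures, both required | Failures, at least one required |
|---|---|---|---|---|
| 30 | 4 | 3 | 7/37 = 18.9% (pass) | 3/37 = 8.1% (pass) |
| 29 | 5 | 3 | 8/37 = 21.6% (fail) | 3/37 = 8.1% (pass) |

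One more single-blanket patient separates the two verdicts.

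**How likely is a reversal?** The documents give no retention rates, so these are assumptions shown as a range. Let q be the probability that a given blanket is applied and stays on through the trauma bay, and ρ the within-patient correlation between the two blankets. Then

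P(both) = q² + ρq(1 − q), and P(at least one) = 2q − P(both).

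The chance of passing is P(X ≤ 7), with X binomial(37, 1 − adherence).

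| q | ρ | P(both) | P(at least one) | Pass, both | Pass, at least one |
|---|---|---|---|---|---|
| 0.85 | 0 | 0.7225 | 0.9775 | 15% | 100% |
| 0.85 | 0.5 | 0.786 | 0.914 | 45% | 99% |
| 0.85 | 0.8 | 0.8245 | 0.8755 | 68% | 92% |
| 0.85 | 1 | 0.85 | 0.85 | 82% | 82% |
| 0.90 | 0 | 0.81 | 0.99 | 59% | 100% |
| 0.90 | 0.5 | 0.855 | 0.945 | 84% | 99.9% |
| 0.95 | 0 | 0.9025 | 0.9975 | 98% | 100% |

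**The same question without a correlation parameter.** Split patients into both, one only and none. The verdicts are opposite when none ≤ 7 and none + one only ≥ 8 (n = 37), or none ≤ 5 and none + one only ≥ 6 (n = 29). The trinomial probabilities are:

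| None | One only | n = 37 | n = 29 |
|---|---|---|---|
| 5% | 5% | 0.03 | 0.06 |
| 5% | 10% | 0.18 | 0.26 |
| 5% | 15% | 0.47 | 0.53 |
| 5% | 20% | 0.74 | 0.77 |
| 10% | 5% | 0.15 | 0.20 |
| 10% | 10% | 0.44 | 0.47 |
| 10% | 15% | 0.71 | 0.71 |
| 10% | 20% | 0.88 | 0.84 |

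**The case against.** The strongest reply is that two different outcomes are being compared. Criterion 2 mirrors Summary outcome (2), adherence in the trauma bay. The at-least-one wording belongs to outcome (4), maintenance across phases, to which Section 6.1 attaches no threshold. A reader might infer that the plan tests the at-least-one definition against the 20% cut; it does not say so. On this view the intervention is always two blankets, the only trauma-bay item with a number is in Section 3.3, and criterion 2 is most naturally read as both. The rule in Section 9.1 defines an analysis set, not adherence.

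Much of this stands. But outcome (4) names the trauma bay in its phase list, so the texts do disagree on the phase that criterion 2 governs. Even if both is the natural reading, it is not written down, and the status of temporary removal stays open.

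A second reply is that Section 5.4.1 is a list of information to collect, not the case report form, which is not in the documents. That is fair: the limitation can be claimed only for the items as listed. Visit 1 also asks when the blanket was placed and why it was not applied, and Visit 2 asks why it was removed, but none of these gives a count.

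Third, the contrast of 15% with 100% needs independent blankets. Both are opened and handed over together, so positive correlation is plausible, although a procedure may displace only one. The contrast is one end of a range.

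**Conclusion.** The point holds as an unresolved definition in a pass/fail rule, together with listed data items that cannot support the two-blanket outcomes of Section 3.3. With 37 intervention patients the line falls between 7 and 8 failures, so a handful of single-blanket patients can reverse criterion 2.

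How likely that is cannot be fixed from the documents. At 85% retention per blanket, the chance of passing under both versus at least one runs from 15% against 100% (independent) through 45% against 99% (correlation 0.5) to 82% under either definition (correlation 1). At 95% retention it is about 98% against 100% even if independent, and the choice hardly matters.

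Two stronger readings are not supported. A reader might infer that this ambiguity alone decides whether the trial is feasible; but criterion 2 is one of three criteria in Section 6.1, and Section 3.2 names enrolment of 74 patients as the primary feasibility outcome. A reader might also infer that the sample size is wrong; on this point it is not. The change should be made, since it is cheap before enrolment, whereas a count that was not recorded may not be recoverable afterwards.

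**What to change.** 1. Reconcile the planned-use row and the Study Outcomes row of the Summary, Section 3.3 and Section 6.1 to one adherence definition per phase of care.
2. In criterion 2, state how many blankets must be applied and maintained for a patient to count as adherent, and whether temporary removal for a procedure counts as failure to maintain. Report the other definition descriptively.
3. At Visit 1 and Visit 2, replace the yes/no blanket items with the number of blankets on the patient (0, 1 or 2) at each check. Either definition can then be derived.

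Which definition to adopt is for the investigators; nothing here proposes a clinical rule for blanket use. The cost is aligned wording in four places and a slightly longer field in the case report form, with no change to the sample size.

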2.0 INTRODUCTION

This study document is the protocol for a research study involving human participants. This study is to be conducted according to Canadian and international standards, and in compliance with the International Conference on Harmonization Good Clinical Practice E6 (ICH-GCP), World Medical Association Declaration of Helsinki: Ethical Principles for Medical Research Involving Human Participants, as well as applicable regulatory and institutional requirements and research policies.

2.1 Background

2.1.1 Hypothermia and Mortality in Trauma

Massively bleeding hypothermic trauma patients have 2.7-fold higher odds of mortality in the first 24 hours of hospital admission, increased length of stay, and increased need for transfusion.¹⁻⁷ Hypothermia is independently associated with mortality in traumatically injured patients due to its negative physiologic effects on hemostasis, cardiorespiratory and renal function.⁸ Despite this, a retrospective quality review at our institution found that approximately 30% of trauma patients will have hypothermia despite the treatment provided.⁹

2.1.2 Conventional re-warming strategies for in-hospital patients

The most common first-line active surface rewarming strategies involve the use of a combination of forced air warming blankets (FAWB), and warmed blankets. Unfortunately, these strategies are cumbersome and ineffective,¹⁰ particularly during the initial hours of admission where multiple transfers occur.¹¹ FAWB requires continuous power, which limits portability. In addition, thermally warmed blankets require interchange at frequent intervals.

2.1.3 Chemical warming blankets

Prehospital, military, and intraoperative studies have suggested chemical warming blankets as a pragmatic strategy.^{8, 12} A recent pilot study (manuscript under review) at our institution demonstrated feasibility of using the Ready-Heat® (TechTrade LLC, Orlando, FL, USA) chemical heating blanket in the initial phases of hospital care in bleeding trauma patients requiring a mass hemorrhage protocol (MHP). In this pilot study, the blanket was applied within a median time of 23 minutes. These chemical blankets generate an oxygen-activated exothermic effect in 8-15 minutes, providing warmth over 8 hours (up to 40 degrees Celsius). These blankets carry the advantage of portability without electricity requirement. Furthermore, in conjunction with other strategies, they provide a superior surface rewarming strategy for patients at high risk of developing hypothermia. STAYWARM-2 will be the first randomized controlled trial performed in-hospital to evaluate a self-warming blanket to address hypothermia in massively bleeding trauma patients within the initial hours post hospital arrival.

2.2 Current Proposal and Rationale

We propose a phase I, single centre, pilot, feasibility, prospective, open-label (with blinded outcome assessors) RCT. STAYWARM-2 aims to examine the impact of the Ready-Heat® warming blanket on the temperature of injured patients receiving a massive transfusion. Current warming strategies increase the logistical difficulty of transferring patients (which is frequent during the initial hours of trauma care) or must be changed at frequent intervals. Chemical blankets that provide continuous heat address these two challenges. This has potential to reduce the overall workload of direct care clinicians, freeing them for other patient care duties. Additionally, the intervention may achieve enhanced thermoregulation compared to the current strategy (as demonstrated in the prehospital literature), which can provide better care and better patient comfort (hypothermia causes patient discomfort¹⁵) and avoid the clinical

complications related to hypothermia. Findings from this preliminary study will provide data for a future CIHR or military grant to launch a larger randomized controlled trial in the prehospital/in-hospital trauma settings, to improve the care of patients at risk of developing hypothermia.

2.3 Study Impact and Benefit

The study will provide knowledge on feasibility and efficacy of using the chemical blankets during these initial hours of hospital care to further support better management of hypothermia. The new evidence generated may be used to inform larger studies (e.g., multicenter trials) in the same setting or in other acute care settings, such as the emergency department and in burn units. Finally, the study will contribute evidence to be applied in studies in the civilian prehospital setting (e.g., land or air Emergency Medical Services) as this setting lacks resources to adequately prevent or treat hypothermia.

3.0 OBJECTIVES AND SCIENTIFIC AIMS

3.1 Study Objectives

1 - To investigate the feasibility of using the Ready-Heat® chemical heating blanket to increase the body temperature by at least 1°C in severely injured trauma patients with activation of a massive hemorrhage protocol (MHP), compared to conventional in-hospital surface rewarming methods (e.g., warmed blankets and/or FAWB) for the first eight hours of blanket application on the patient.

3.2 Primary feasibility outcome:

1 - Feasibility of enrolling the 74 patients over a span of two years.

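### The primary feasibility outcome differs between section 3.2, the synopsis and section 6.1, and nothing says which governs or how the criteria combine

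*Combined protocol and SAP*

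**What the plan says.** **Section 3.2** gives a single primary feasibility outcome: "Feasibility of enrolling the 74 patients over a span of two years".

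**The synopsis (Study Outcomes)** lists four primary outcomes. Item 1 begins "Feasibility of performing a pilot pragmatic randomized controlled trial (RCT) to evaluate effectiveness of the" Ready-Heat blanket in raising temperature by 1°C. Items 2 and 3 are adherence to blanket application in the trauma bay and adherence to temperature measurement. Item 4 is "Feasibility of maintenance of at least one blanket applied throughout the different phases of care". No item gives a recruitment target, although item 1 could loosely include recruitment. The synopsis also says "We will present point estimates of feasibility outcomes with 95% confidence intervals".

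**Section 6.1**, headed as the assessment of the primary outcome, has three rules:
- Rule 1 applies if the intervention does not achieve a rise of at least 1°C "in 80% of patients at eight hours from arrival, the study as it is currently designed will not be deemed feasible".
- Rule 2 applies if the blanket is not applied and maintained "in more than 20% of patients enrolled in the intervention arm throughout the initial trauma bay resuscitation, the study will not be deemed feasible".
- Rule 3 begins "Failure to measure body temperature throughout different phases of care" and applies when this happens in more than 20% of enrolled patients.

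**Section 4.0** hypothesises feasibility according to one primary outcome measure, which it does not name.

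**Section 7.1** sizes the trial on a compliance rate of 80% within ±10 points at 95% confidence: 58 patients in total, raised to 74 for 20% dropout. Compliance is not defined. Recruitment runs until 74 are enrolled; the 24 months in the synopsis and section 5.3.1 is an anticipated duration.

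**Section 7.2** investigates the primary objective through the proportion with a 1°C rise, compared between arms. It names no estimate for enrolment or adherence.

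**The concern.** A feasibility pilot has one main conclusion: feasible or not. Here the outcome that section 3.2 calls primary has no decision rule. The three items that do have decision rules are called efficacy, secondary feasibility and clinical outcomes in section 3. With no statement of precedence and no combination rule, the governing criterion could be settled after the results are known.

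The sample-size argument is also detached. It supports the precision of a proportion that is never identified with any listed outcome, so a reader cannot tell which feasibility estimate the stated ±10 points is meant to describe.

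**Working it through.** **1. The sections side by side**

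| Item | Synopsis | Section 3 | Section 6.1 | Section 7.2 |
|---|---|---|---|---|
| 74 enrolled in two years | no target stated | sole primary (3.2) | no rule | no analysis |
| 1°C rise | within primary item 1 | efficacy (3.4, item 9) | rule 1 | proportion by arm, for the primary objective |
| Blanket in trauma bay | primary item 2 | secondary feasibility (3.3, item 2) | rule 2 | none named |
| Temperature measurement | primary item 3 | clinical (3.5, item 10) | rule 3 | none named |
| Blanket kept through later phases | primary item 4 | secondary feasibility (3.3, items 3 to 7) | no rule | none named |

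No row has the same status in the synopsis, section 3 and section 6.1.

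**2. Can the sections give different answers?**

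Rule 2 is triggered when failures/n exceeds 0.20. Counting all 37 intervention patients:
- 7/37 = 18.9%, not triggered
- 8/37 = 21.6%, triggered

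Rule 3, counting all 74:
- 14/74 = 18.9%, not triggered
- 15/74 = 20.3%, triggered

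Rule 1, if read on the 37 intervention patients, needs 30/37 = 81.1%; 29/37 = 78.4% falls short.

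*Case A.* 74 enrol within two years and 8 of 37 lack the blanket. The outcome in 3.2 is met; 6.1 says not feasible.

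*Case B.* The 74th patient enrols after two years and all three rules in 6.1 are satisfied. The outcome in 3.2 is missed; 6.1 triggers nothing. Section 7.1 allows this, because it continues until 74 are enrolled.

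The denominators are assumptions. Section 10.2 makes patients who decline delayed consent screening failures, and 7.1 expects 20% dropout, but sections 9.0 and 13.1 let data collected before withdrawal be used. With 29 in the arm, rule 2 is triggered at 6/29 = 20.7% (5/29 = 17.2% is not). The figure of 29 is not a floor: section 5.3.2 specifies no blocking, so the arms may be unequal.

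**3. Reproducing section 7.1**

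Inputs from 7.1: p = 0.80, d = 0.10. The formula that matches its output is the exact binomial probability P(0.70 ≤ X/n ≤ 0.90 | p = 0.80).
- n = 57 (X from 40 to 51): 0.95529, as printed
- n = 37 (X from 26 to 33): 0.90329, as printed

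57 becomes 58 for equal arms. For dropout, 29/0.8 = 36.25, so 37 per arm and 74 in total. The arithmetic is sound.

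**4. The same method for one arm**
- n = 58: 0.95288
- n = 37: 0.90329
- n = 29 (X from 21 to 26): 0.83959

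Smallest half-width that reaches 95% by this method:
- n = 37: X must run down to 25, and 0.80 − 25/37 = 0.124, about ±12.5 points
- n = 29: X must run down to 19, and 0.80 − 19/29 = 0.145, about ±14.5 points

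Wald half-width, 1.96 × √(0.16/n):
- n = 37: 0.129
- n = 29: 0.146
- n = 58: 0.103
- n = 74: 0.091

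**The case against.** **Section 7.2 is consistent with the stated objective.** Section 3.1 gives one objective, the feasibility of using the blanket to raise temperature by at least 1°C, and 7.2 analyses exactly that. This stands. A reader might infer that 7.2 is one more contradictory definition of the primary endpoint. The documents do not support that: 7.2 agrees with 3.1 and with rule 1. What it does not match is the outcome in 3.2 and the efficacy label in 3.4.

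**The criteria may be cumulative.** Only 6.1 states decision rules, and neither 3.2 nor 4.0 says that timely enrolment is enough. If the trial must meet the enrolment target and also pass all three rules, Cases A and B are both simply failures. This is a fair reading, but nowhere stated, and the singular measure in 4.0 sits badly with it. A reader might infer that the verdict is bound to reverse between sections; that goes too far.

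**Section 7.1 never promises ±10 points for one arm.** Correct: it says 58 in total. Pooling is coherent, since section 5.6 treats non-use of either the control or the study intervention as noncompliance, and rule 3 covers all enrolled patients. So the sample size is not miscalculated. What remains is that compliance is undefined and that the stated precision does not carry over to rule 2.

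**Nothing is lost from the data.** The synopsis promises estimates with confidence intervals, section 5.3.1 keeps a recruitment log, and section 5.4.1 collects blanket and temperature adherence. This stands; the defect lies in definition and decision rule, not in data collection.

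**Conclusion.** The concern holds, and the text is wrong as written rather than merely short of detail. The same items are primary in the synopsis and 6.1 and non-primary in 3.3 to 3.5; the only primary outcome in 3.2 has no rule in 6.1 and no analysis in 7.2; synopsis item 4 has no rule either.

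The size is a possible change in the trial's main conclusion, for instance at 8 of 37 with timely enrolment. That example assumes that all 37 are counted and that 3.2 is not merely one of several cumulative conditions. No probability of such a conflict can be given from the documents.

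On precision, ±10 points at 95% suits an outcome measured in both arms together. For an outcome confined to the intervention arm the figure is about ±12.5 points at n=37 or ±14.5 at n=29 at a true rate of 80%. A reader might infer from this that the trial is too small; the documents do not support that, because 7.1 claims its precision only for the total.

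**What to change.** Before results are seen:

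1. Choose one set of primary feasibility outcomes and carry it identically through the synopsis and sections 3.2 to 3.5, 4.0, 6.1, 7.1 and 7.2. Which outcomes are primary, including the status of the 1°C rise, is the sponsor's choice.
2. If enrolment of 74 in 24 months stays primary, add it to 6.1 as a criterion and to 7.2 as an analysis.
3. State whether failing any one criterion means not feasible.
4. Define compliance and its denominator in 7.1. If it is an intervention-arm outcome, restate the precision by one method throughout (exact: about ±12.5 points at n=37 and ±14.5 at n=29; Wald: ±12.9 and ±14.6) rather than enrol more.
5. Separately, synopsis item 4 asks for at least one blanket through all phases, while 3.3 asks for two in most locations and at least one in the OR or IR suite. These must be reconciled.

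The cost is amendment wording and, for intervention-arm outcomes, a less favourable stated precision. The sample size stays at 74.
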